**Signature**

**Date**

## PROTOCOL SYNOPSIS

Sponsor: BioMed Valley Discoveries, Inc.	Investigational Product: BVD-523	Developmental Phase: Phase 1
Title of Study:  Phase 1 Dose-Escalation, Safety, Pharmacokinetic and Pharmacodynamic Study of BVD-523 in Patients with Advanced Malignancies		
Protocol Number:  BVD-523-01		
Indication:  Advanced malignancies		
Objectives:  Primary objective:  To define the safety and tolerability of BVD-523 in patients with advanced malignancies by determining the dose-limiting toxicities (DLT), the maximum tolerated dose (MTD), and the recommended Phase 2 Dose (RP2D).  Secondary objectives:  To determine the pharmacokinetic profile of BVD-523 and selected metabolites in patients with advanced malignancies.  To investigate any preliminary clinical effects on tumor response assessed by physical or radiological exam (RECIST 1.1).  Exploratory objective(s):  To evaluate pharmacodynamic marker (biomarker) measures.		
Methodology:  Open-label, dose-escalation, multicenter Phase 1 study with dose-escalation phase (Part 1) and cohort expansion phase (Part 2).		

Sponsor: BioMed Valley Discoveries, Inc.	Investigational Product: BVD-523	Developmental Phase: Phase 1
Diagnosis and Criteria for Inclusion:		
Patients eligible for inclusion in this trial have to fulfill all of the following criteria:		


1. Provide signed and dated informed consent prior to initiation of any study-related procedures that are not considered standard of care (SOC).

2. Male or female patients aged <math>\geq 18</math> years.

3. Patients with metastatic or advanced-stage malignant tumor, confirmed histologically, for whom no therapy exists that would be curative.

4. ECOG performance status of 0 (fully active, able to carry out all pre-disease activities without restriction) or 1 (unable to perform physically strenuous activity but ambulatory and able to carry out work of a light or sedentary nature), measured within 72 hours before the start of treatment.

5. Predicted life expectancy of <math>\geq 3</math> months.

6. Adequate renal function [creatinine <math>\leq 1.5</math> times ULN (upper limit of normal)] or GFR of <math>\geq 50</math> mL/min.

7. Adequate hepatic function [total bilirubin <math>\leq 1.5</math> times ULN; AST (aspartate transaminase) and ALT (alanine transaminase) <math>\leq 3</math> times ULN or <math>\leq 5</math> times ULN if due to liver involvement by tumor.

8. Adequate bone marrow function (hemoglobin <math>\geq 9.0</math> g/dL; platelets <math>\geq 100 \times 10^9</math> cells/L; absolute neutrophil count <math>\geq 1.5 \times 10^9</math> cells/L).

9. Adequate cardiac function, <math>\geq</math> institutional lower limit of normal e.g., left ventricular ejection fraction (LVEF) of <math>> 50\%</math> as assessed by multi-gated acquisition (MUGA) or ultrasound/echocardiography (ECHO); corrected QT interval (QTc) <math>< 470</math> ms.

10. Contraception:

• For women: Negative pregnancy test for females of child-bearing potential; must be surgically sterile, postmenopausal (no menstrual cycle for at least 12 consecutive months), or compliant with a medically approved contraceptive regimen during and for 3 months after the treatment period. Abstinence is not considered an adequate contraceptive regimen.

• For men: Must be surgically sterile, or compliant with a medically approved contraceptive regimen during and for 3 months after the treatment period.

11. Willing and able to participate in the trial and comply with all trial requirements.

12. For Part 2 of the Study ONLY:

• Patient must be diagnosed with specific tumor types and histologies.

• Patient must bear tumors that harbor specific classes of genetic mutations.

• Patients must have measurable disease by RECIST 1.1.

		

Sponsor: BioMed Valley Discoveries, Inc.	Investigational Product: BVD-523	Developmental Phase: Phase 1

Criteria for Exclusion:
 
Patients who fulfill one or more of the following criteria will not be eligible for inclusion in this trial:
 

1. Gastrointestinal (GI) condition that could impair absorption of study medication (specific cases e.g., remote history of GI surgery, may be enrolled after discussion with the medical monitor) or inability to ingest study medication.

2. Uncontrolled or severe intercurrent medical condition.

3. Known uncontrolled brain metastases. Stable brain metastases either treated or being treated with a stable dose of steroids/anticonvulsants, with no dose change in the previous 4 weeks, can be allowed.

4. Any cancer-directed therapy (chemotherapy, hormonal therapy, biologic or immunotherapy, etc.) within 28 days or 5 half-lives, (whichever is shorter). Patients previously treated with radiotherapy must have recovered from the acute toxicities associated with such treatment.

5. Major surgery within 4 weeks prior to first dose.

6. Any use of an investigational drug within 28 days or 5 half-lives (whichever is shorter) prior to the first dose of BVD-523. A minimum of 10 days between termination of the investigational drug and administration of BVD-523 is required, unless a dose escalation of BVD-523. In addition, any drug-related toxicity except alopecia should have recovered to Grade 1 or less.

7. Pregnant or breast-feeding women.

8. Any evidence of serious active infections.

9. Any important medical illness or abnormal laboratory finding that would increase the risk of participating in this study (based on the investigator's judgment).

10. A history or current evidence/risk of retinal vein occlusion (RVO) or central serous retinopathy (CSR).

11. Concurrent therapy with any other investigational agent.

12. Concurrent therapy with drugs known to be strong inhibitors of CYP1A2, CYP2D6 and CYP3A4, or strong inducers of CYP3A4 (for list of non-permitted drugs, see Appendix 1).

13. Concomitant malignancies or previous malignancies with less than 2 years disease-free interval at the time of enrollment (except non-melanoma skin cancer, cervical cancer in situ, prostate cancer with undetectable PSA). Other concurrent malignancies that are indolent and do not require active treatment must be discussed with the medical monitor prior to enrollment.

		

Sponsor: BioMed Valley Discoveries, Inc.	Investigational Product: BVD-523	Developmental Phase: Phase 1
Test Product, Dose and Mode of Administration:  Part 1: BVD-523, starting at 10 mg, with escalating dose levels, twice daily for 21 days, oral.  Part 2: BVD-523, recommended Phase 2 dose (RP2D), twice daily for 21 days, oral.		
Concomitant Medications:  Necessary supportive care such as antiemetics, antidiarrheals, etc., will be allowed. Certain other medications such as stable doses of steroids for brain metastases may also be allowed. Drugs that are strong inhibitors of CYP1A2, CYP2D6 and CYP3A4, or strong inducers of CYP3A4, will not be allowed during the study (for list of non-permitted drugs, see Appendix 1 ).		
Study Duration:  Part 1: 10 to 18 months, Part 2: 18 to 24 months		
Criteria for Evaluation:  Safety: Vital signs, physical examination, ophthalmology examination, clinical chemistry, hematology, urinalysis, electrocardiograms (ECG), and Holter monitoring.  Efficacy: Tumor measurements (anti-tumor activity as evaluated using RECIST 1.1).  Pharmacokinetics: Blood, urine, and tissue biopsy (as indicated) BVD-523 and selected metabolite concentration levels.  Pharmacodynamics: Evaluation of multiple biomarkers to characterize drug response (pRSK, pERK, Ki67, Caspase-3, and circulating tumor DNA). Additional biomarkers may be identified and measured as appropriate. Tumor genotyping by DNA analysis will be performed to identify somatic alterations, relying on either available archived tissue or freshly-collected samples.		

Sponsor: BioMed Valley Discoveries, Inc.	Investigational Product: BVD-523	Developmental Phase: Phase 1
Statistical Methods: 
The sample size for Part 1 of this study was determined by clinical rather than statistical considerations. Approximately 40 patients will be treated in Part 1 of this study (Dose Escalation Phase) to establish dose limiting toxicities (DLT), maximum tolerated dose (MTD), and the recommended Phase 2 dose (RP2D).
 
The purpose of Part 2 of this first in human research is to document that there is some evidence of a response. Upon completion of Part 1 of this study, up to approximately 105 evaluable patients with certain cancer types and/or characterized genetic alterations will be treated with the RP2D (which may be the same or lower than the MTD). The observation of DLTs in more than 33% of patients in any Part 2 cohort with at least 6 patients enrolled at any time during Part 2 will trigger temporary stopping of patient enrollment and revision of the definition of the MTD and potentially RP2D in the specific cohort. Subsequent patients will be treated with a dose lower than the initial MTD and this dose will be determined in discussion with the Clinical Investigators, the Medical Monitor, and the Sponsor.
 
Enrollment of up to 15 evaluable patients in each cohort provides an 80% probability of seeing at least one positive response if the true response rate is at least 10%. Allowing for a low response rate in these patient cohorts is appropriate based on unmet medical need.
		

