A unique array of oncogenic mutations cluster in the mitogen-activated protein kinase, or MAPK, pathway, a key signal transduction cascade that controls cell-growth signaling in many tissues (Sebolt-Leopold 2004a, Chang 2003, Hilger 2002, Kohno 2003, Smalley 2003). Activating mutations in RAS GTPase family members are found in ~30% of all cancers (Bos 1989), with particularly high incidence in pancreatic (90%) (Almoguera 1988) and colon (50%) cancer (Salhab 1989). Activating somatic missense mutations of BRAF are frequent in melanomas (up to 80%) (Pollock 2002, Gorden 2003), papillary thyroid (36%) (Xu 2003), colon (up to 18%) (Ikenoue 2003), and ovarian (14%) (Hsu 2004) cancers. Less frequently, activating mutations have also been observed in MEK family kinases, which are the direct substrates of RAF kinases. MEK kinases phosphorylate and activate the ERK kinase gene family. ERK kinases phosphorylate numerous proteins that act as MAPK pathway “effectors”; these substrates directly promote cell division, reduce cell death, and increase cell motility and cell differentiation (Chang 2003, Sebolt-Leopold 2004b). To date, spontaneous activating mutations in ERK kinases have not been observed in human cancers. Nonetheless, abundant ERK phosphorylation reflecting elevated MAPK signaling is frequently observed in cancer contexts where extracellular growth factors are elevated (Wan 2004), or where activating mutations in RAS, BRAF, or MEK genes have occurred.

In this setting, therapies targeted against MAPK pathway components have been rationally applied in cancers that show activation of the signaling cascade following genetic mutation. Notably, vemurafenib (ZELBORAF®), is an inhibitor of mutated BRAF that, when dosed in patients with metastatic melanoma harboring specific BRAF activating mutations, induces tumor regression and improves overall survival in this defined patient population (Flaherty 2010, Sosman 2012, Chapman 2011).

The development of additional therapies that can modulate MAPK pathway activity in cancer is desirable for several reasons. First, all drugs exhibit a unique spectrum of side effects that often influences their therapeutic utility. Despite some findings suggestive of mechanism-related events, the incidence and severity of both BRAF and MEK inhibitor

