The classic 3 + 3 design will be conducted as follows. Initially, 3 patients will be enrolled to a cohort; the occurrence of a single drug-related DLT in one of these 3 patients will prompt enrollment of up to an additional 3 patients to that same cohort i.e., 3 + 3. When more than 1 DLT occurs in  $\leq$  6 patients in a dosing cohort, dose escalation will be stopped and this dose level will be identified as the non-tolerated dose. Doses between the non-tolerated dose and the preceding lower dose, where  $\leq$  1 DLT occurred, may be explored to define the MTD. This strategy allows for a rigorous determination of MTD, especially if the dose increase that resulted in determination of the non-tolerated dose is relatively large (i.e.,  $>$  50%).

At any time during the study, the Sponsor and Investigators may request that cohorts should be enlarged or that exploration of intermediate doses between 2 planned escalation steps should be explored. Such requests will be discussed with the Sponsor and Medical Monitor, and should be based on all data existing at that time, including determinations of pharmacokinetics, pharmacodynamics, and cumulative toxicity. Before each escalation, investigators will be consulted to ensure that all involved agree with the escalation decision.

In addition, once the RP2D is defined, intra-patient dose escalation to the RP2D will be allowed after a patient has completed at least 1 cycle at their assigned dose and only if the patient has experienced no toxicity above Grade 1, upon request by the PI and discussion with the Medical Monitor and the Sponsor.

Part 2 – Cohort-expansion Phase: Additional patients with particular tumor types and/or cancers harboring specific genetics will be recruited for treatment at the Recommended Phase 2 Dose (RP2D). Patients must have measurable disease by RECIST 1.1. Patients will receive twice daily oral doses of BVD-523 in 21-day treatment cycles until disease progression, unacceptable toxicity, or another withdrawal criterion is met (Section 7.2). Treatment cycles will occur consecutively without interruption except when necessary to manage toxicities.

Total enrollment for Part 2 is targeted at approximately 105 evaluable patients. Patients will be enrolled into 1 of 7 treatment groups. Group assignments are made according to the following disease characteristics, which correspond to specific inclusion and exclusion criteria for Part 2.

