- Group 1: Patients with BRAF mutated cancer, except those with colorectal or non-small cell lung cancers, not previously treated with BRAF and/or MEK inhibitors; n ≤ 15
- Group 2: Patients with BRAF mutated colorectal cancer, not previously treated with BRAF and/or MEK inhibitors; n ≤ 15
- Group 3: Patients with BRAF mutated melanoma who have progressed or are refractory to BRAF and/or MEK inhibitors; n ≤ 15
- Group 4: Patients with NRAS mutated melanoma, not previously treated with BRAF and/or MEK inhibitors; n ≤ 15
- Group 5: Patients with MEK mutated cancer, not previously treated with BRAF and/or MEK inhibitors; n ≤ 15
- Group 6: Patients with BRAF mutated non-small cell lung cancer, not previously treated with BRAF and/or MEK inhibitors; n ≤ 15
- Group 7: Patients with ERK mutated cancer, not previously treated with BRAF and/or MEK inhibitors; n ≤ 15

Initial enrollment targets for each group may be modified to respond to accrued safety, clinical effect, pharmacokinetic, and pharmacodynamic data. The decision to expand enrollment in one or more groups will be made through consultation among the Principal Investigators, the Medical Monitor and the Sponsor.

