#### 3.1.4.2 Definition of Dose Limiting Toxicity (DLT)

DLT is defined as BVD-523 related toxicity in the first 21 days of treatment that results in:

- $\geq$  Grade 4 hematologic toxicity for > 1 day

- Grade 3 hematologic toxicity with complications e.g., thrombocytopenia with bleeding
- $\geq$  Grade 3 non-hematologic toxicity, except untreated nausea, vomiting, constipation, pain, and rash (these become DLTs if the AE persists despite adequate treatment), a doubling of AST/ALT in patients with grade 2 ALT/AST at baseline
- A treatment interruption exceeding 5 days (or an interruption exceeding 7 days for rash, despite adequate treatment) in Cycle 1 (or inability to begin Cycle 2 for > 7 days) due to BVD-523-related toxicity

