## **4 SELECTION OF PATIENTS**

### **4.1 NUMBER OF PATIENTS**

In this Phase 1 study up to 40 patients with advanced solid tumors will be enrolled in Part 1. One to six patients per treatment cohort will be assigned to receive sequentially higher oral doses of BVD-523.

The purpose of Part 2 of this first in human research is to document that there is some evidence of a response. Upon completion of Part 1 of this study, up to approximately 105 evaluable patients with certain cancer types and/or characterized genetics will be assigned to 1 of 7 treatment arms and treated with the RP2D determined in Part 1 (which may be the same or lower than the MTD). The observation of DLTs in more than 33% of patients in any Part 2 cohort with at least 6 patients enrolled at any time during Part 2 will trigger temporary stopping of patient enrollment and revision of the definition of the MTD and potentially RP2D in the specific cohort. Subsequent patients will be treated with a dose lower than the initial MTD and this dose will be determined in discussion with the Clinical Investigators, the Medical Monitor, and the Sponsor.

Enrollment of up to 15 evaluable patients in each cohort provides an 80% probability of seeing at least one positive response if the true response rate is at least 10%. Allowing for a low response rate in these patient cohorts is appropriate based on unmet medical need.

In Part 2 of the study, patients who withdraw at any time preceding the 1st protocol-specified tumor measurement evaluation at the end of Cycle 2 (except for study drug-related AE) will be replaced.

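### No numerical DLT rule requires a Part 2 group to pause before its sixth patient, even when a breach at six is already certain, and a group that ends with five or fewer patients is never covered

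*Protocol*

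**What the plan says.** The Protocol Synopsis (Statistical Methods) sets one DLT-count rule for Part 2: "DLTs in more than 33% of patients in any Part 2 cohort with at least 6 patients enrolled at any time during Part 2". Sections 4.1 and 10.1.2 repeat it with the same minimum of six. In the Synopsis, meeting the condition "will trigger temporary stopping of patient enrollment and revision of the definition of the MTD and potentially RP2D in the specific cohort". The design and sample-size sections of the SAP (3.1 and 4) do not carry the rule.

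Group sizes have a ceiling but no floor, for example "Group 7: Patients with ERK mutated cancer, not previously treated with BRAF and/or MEK inhibitors; n ≤ 15" (Protocol 3.1.2). On how common such tumors are, Protocol 1.3 says "To date, spontaneous activating mutations in ERK kinases have not been observed in human cancers". The Introduction, however, says that ERK mutations were recently reported and puts MEK mutations at 8% of melanomas.

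The DLT definition in 3.1.4.2 opens "DLT is defined as BVD-523 related toxicity in the first 21 days of treatment that results in". In Part 1, when more than one DLT occurs in six or fewer patients "in a dosing cohort, dose escalation will be stopped and this dose level will be identified as the non-tolerated dose" (3.1.2). That rule governs dose escalation. The safety review meetings in 3.3 are likewise tied to dose escalation.

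Some safeguards apply at any group size. Group targets may be changed in response to safety data (3.1.2). The SMC reviews serious adverse events and the safety of each dose level (3.2), and must review a drug-related serious event at once (7.1). One related death or anaphylaxis suspends the study (7.1). The sponsor may terminate at any time (11.10).

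**The concern.** A DLT count cannot fall as patients are added. Once a group has enough DLTs to exceed 33% at six, patients up to the sixth add nothing to the rule's answer, yet the rule cannot act until they are enrolled. A group that closes at five is never tested against the threshold, whatever its count.

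The other safeguards do not fill this gap with a count. A DLT need not be a serious adverse event: a related treatment interruption of more than five days in Cycle 1, or a Grade 3 non-hematologic toxicity, can be a DLT under 3.1.4.2 without meeting the seriousness definition in 9.2. Safety at the recommended dose is part of the primary objective, and this is the only numerical DLT rule for Part 2. What is at stake is a small number of avoidable exposures per group, and the absence of any count-based rule in groups that accrue poorly.

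**Working it through.** **Inputs.** Threshold above 33% and minimum of six enrolled: Synopsis, 4.1, 10.1.2. Seven groups of at most 15, no minimum: 3.1.2. DLT window of 21 days: 3.1.4.2. The documents give no true DLT rate p, so p is assumed from 10% to 50%. Patients are taken as independent, entering one at a time, with each DLT known before the next patient enters.

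**1. The plan's own figure.** The only operating figure stated for a Part 2 group is 80% for at least one response in 15 at a 10% response rate: 1 − 0.9^15 = 0.794, which agrees. No operating figure is given for the DLT trigger.

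**2. Count needed at six.** 2/6 = 0.3333 exceeds 0.33 but does not exceed one third; 3/6 = 0.50 exceeds both. So k = 2 if 33% is literal and k = 3 if it means one third. The protocol does not say which. The literal reading fits Part 1 better: 2 of 6 makes a dose non-tolerated, and the MTD (3.1.4.1) allows at most 33%. The two agree at 2 of 6 only if 2/6 exceeds 33%.

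**3. Chance that a breach at six is certain within five patients.** With X ~ Binomial(5, p):
- P(X ≥ 2) = 1 − (1−p)^5 − 5p(1−p)^4. At p = 0.33: 1 − 0.1350 − 0.3325 = 0.5325.
- P(X ≥ 3) subtracts a further 10p²(1−p)³. At p = 0.33: 0.5325 − 0.3275 = 0.2050.

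**4. Further patients before the rule can act.** The k-th DLT falls on patient m with probability C(m−1, k−1) p^k (1−p)^(m−k), and 6 − m patients (including the sixth) may then still enter. For k = 2 and p = 0.33, the terms for m = 2 to 5 are 0.1089×4 + 0.1459×3 + 0.1467×2 + 0.1310×1 = 1.30. Divided by 0.5325, the mean when certainty comes early is 2.44.

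| True DLT rate | Certain by patient 5 (literal / one third) | Mean further patients, if certain early | Mean further patients, all groups |
|---|---|---|---|
| 20% | 0.263 / 0.058 | 2.24 / 1.61 | 0.59 / 0.09 |
| 33% | 0.533 / 0.205 | 2.44 / 1.70 | 1.30 / 0.35 |
| 40% | 0.663 / 0.317 | 2.56 / 1.77 | 1.70 / 0.56 |
| 50% | 0.813 / 0.500 | 2.77 / 1.88 | 2.25 / 0.94 |

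The last column is the product of the two before it. The maximum is 4 further patients (2 DLTs in the first 2, literal) or 3 (3 in the first 3, one third).

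**5. Groups that stop at five or fewer.** The chance of a trigger is zero at every p, including 5 of 5.

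**6. Effect of pausing as soon as the breach is certain.** In a group that would reach 15, the chance of ever triggering is the same with and without the early pause, because the count at six is already fixed. At p = 10%, 20%, 33%, 40% and 50% it is 0.129, 0.420, 0.780, 0.896 and 0.975 (literal), or 0.044, 0.254, 0.646, 0.811 and 0.944 (one third). In a group that would end at five, it rises from zero to the step 3 value: 0.082 at 10% and 0.263 at 20% (literal), or 0.009 and 0.058 (one third).

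**The case against.** A reader might infer that a group must go on enrolling to six. The documents do not say so. The rule fixes when a pause is mandatory and does not forbid an earlier one; 3.1.2 lets targets respond to safety data, and 11.10 lets the sponsor stop at any time. A reader might also infer that this is the only numerical safety rule in Part 2. It is not, because one related death or anaphylaxis suspends the study at any group size. Nor does the Part 1 count contradict it: that rule governs escalation into untested doses, which is a different decision.

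A minimum of six is defensible in itself. It equals a full 3+3 cohort, guards against small-number noise, and applies to a dose already studied in Part 1. Because the recommended dose is at or below an MTD defined by at most 33% DLTs, rates of 33% to 50% are the unfavorable end, and at 20% the effect is small. With a 21-day window and up to 15 sites, several patients may be on treatment before any DLT is known, so fewer entries are avoidable than step 4 suggests. No document forecasts a group ending below six, and the protocol's statements on ERK mutations point both ways.

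All of this limits the size of the point. It does not supply a DLT count for a group of five or fewer, or a reason to wait for a result that is already fixed. One objection shapes the remedy. The existing trigger also leads to MTD/RP2D revision and a lower dose, so moving the whole trigger earlier would mandate a dose change after as few as two patients. The change should therefore stop at the enrollment pause.

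**Conclusion.** The point holds in limited form. No numerical DLT rule requires a pause before the sixth patient in a Part 2 group, even when exceeding the threshold at six is certain, and a group that ends below six has no such rule at all. In those cases a pause depends on discretion or on event-based rules that need not capture a DLT.

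Over true rates of 20% to 50%, the breach is certain within five patients in 26% to 81% of groups (literal) or 6% to 50% (one third). When that happens at rates of 33% to 50%, a mean of 2.4 to 2.8 (literal) or 1.7 to 1.9 (one third) further patients could enter. Averaged over all groups this is about 1.3 or 0.35 patients at 33%, and 0.6 or 0.1 at 20%. These figures are per group and rest on assumed DLT rates and strictly sequential entry, so the step 4 counts are upper figures for what is avoidable. The gap is worth closing because closing it is cheap; it does not mean that the plan compels enrollment or leaves small groups without any safety oversight.

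**What to change.** Keep the sponsor's 33% threshold and state whether 2 of 6 exceeds it. In the Synopsis, 4.1 and 10.1.2, add that before six patients are enrolled, enrollment in the cohort is paused for SMC review as soon as its DLT count already guarantees that the threshold will be exceeded at six.

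Leave any MTD, RP2D or dose consequence to the existing discussion among the Clinical Investigators, the Medical Monitor and the Sponsor. The sponsor should also reconcile the dose wording: the Synopsis and 4.1 describe later patients relative to the initial MTD, and 10.1.2 relative to the initial RP2D. This review takes no position on which is right.

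The cost is one added sentence and one clarification in three places, with no added patients or procedures. With sequential entry, a cohort that would reach six is paused on the same outcomes as now, only sooner. The downside is that groups ending below six can now be paused: for a five-patient group the chance is about 8% at a true rate of 10% and 26% at 20% (literal), or about 1% and 6% (one third).
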